## 4.2 Statistical analyses

Descriptive statistics such as safety profile/adverse events and demographic data will be reported as the interquartile range (median  $\pm$ IQR). Data from the WMC, Low-dose CT and breath test will be analysed using repeated measures regression with the intervention (FMT or placebo) as random effect.

The final statistical analysis plan, providing details of the analysis and presentation of results, will be finalised before initiation of any statistical analysis. Patients considered for the evaluation of safety and efficacy will be defined in the statistical analysis plan. Statistical analysis will be performed only after unblinding.

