## 2.4.2 Secondary endpoints

Patient-reported outcomes are obtained from the bowel habit diary. Each patient fills out the diary every day for one week at baseline, for one week starting at each day of the two interventions

and for one week at the follow-up at week 26. Bivariate comparions are made, comparing differences between FMT and placebo at a) Baseline vs first intervention, b) Baseline vs second intervention, c) Baseline vs longterm follow-up (week 26) for the following variables:

- 1. Median stool consistency (Bristol scale)
- 2. Number of passages of hard stools (BS 1-2)
- 3. Number of passages of liquid stools (BS 6-7)
- 4. Median number of bowel openings per 24 hours
- 5. Number of nightly bowel openings (from bedtime until morning)
- 6. Number of episodes with involuntary defaecation
- 7. Glycemic control measured by patient reported use of insulin (IE)

Patient-reported measures from the schedule of side effects and telephone call 1 week after each intervention

- 8. Mild adverse events (grade 1) following FMT or placebo assessed by CTCAE v5.0
- 9. Adverse events in week 5-8
- 10. Serious adverse events during longterm follow-up

Patient-reported outcomes from questionnaires completed at baseline and 4 weeks after each intervention period and at 26 weeks follow-up. Bivariate comparisons baseline vs week 4, baseline vs week 8, baseline vs week 26:

- 11. Change in Gastrointestinal syndrome rating scale irritable bowel version questionnaire (GSRS-IBS)
- 12. Change in patient assessment of upper gastrointestinal symptom severity index (PAGI-SYM)
- 13. Change in irritable bowel syndrome impact scale (IBS-IS)

Objective measures from the wireless motility capsule performed at baseline and 4 weeks after each intervention period:

- 14. Transit time through the small intestine
- 15. Colonic transit time
- 16. pH drop from the small intestine to the colon

Objective measures from the low-dose CT scan performed at baseline and 4 weeks after the first intervention period:

- 17. Volume of the a) small intestine and b) the colon
- 18. Volume of gas in a) the small intestine and b) the colon

Objective measures from the breath test performed at baseline and 4 weeks after the first intervention period:

19. Rise in hydrogen PPM measured in breath test for small intestinal bacterial overgrowth

Microbiota analysis on faecal samples collected at baseline and 4 weeks after each intervention period:

20. Alpha-diversity of faecal microbiota, 16S

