# 3.0 Methods and their justification

## 3.1 Study design

The study is a 8-week, randomised, double-blinded, placebo-controlled pilot trial of oral FMT versus placebo in patients with DM1 and severe GI neuropathy. The intervention period consists of a first 4 weeks where patients receive either FMT or placebo and a second 4 weeks where all patients receive FMT (Figure 1 and 2). The patients will undergo the investigations before and after each 4-week period. When the patients have completed the study period, they will be contacted by telephone every second month for two years. They will be asked about their gastrointestinal symptoms. The patients will be offered further treatment with FMT, if they experience relapse of symptoms and a score of or above 40 in the GSRS-IBS questionnaire.

The design is chosen to allow the evaluation of the safety and tolerability of FMT in patients with DM1. We will also be able to evaluate if FMT is superior to placebo, how it affects the intestinal microbiota and if the effects of two doses of oral FMT is superior to one dose.

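### The regression for motility-capsule, CT and breath-test data makes the two-level treatment a random effect, so it does not deliver the FMT-minus-placebo difference with a confidence interval

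*Protocol*

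**What the plan says.** Protocol section 4.2 (Statistical analyses) gives one sentence on the model for the three objective tests: their data "will be analysed using repeated measures regression with the intervention (FMT or placebo) as random effect". It names no fixed treatment term. The same section leaves further detail to a statistical analysis plan that is to be final before any analysis starts.

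Section 2.4.2 (Secondary endpoints) lists what the model must handle.
- WMC, endpoints 14 to 16: "Objective measures from the wireless motility capsule performed at baseline and 4 weeks after each intervention period", so one baseline and two later measurements.
- CT, endpoints 17 and 18: "Objective measures from the low-dose CT scan performed at baseline and 4 weeks after the first intervention period", so one baseline and one later measurement.
- Breath test, endpoint 19: the same two time points as CT.

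Section 3.1 (Study design) describes a trial of "oral FMT versus placebo in patients with DM1 and severe GI neuropathy" and states the purpose of the comparison: "We will also be able to evaluate if FMT is superior to placebo". It also describes "a second 4 weeks where all patients receive FMT".

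The other comparisons in section 2.4.2 do not cover endpoints 14 to 19. For the diary the text is "Bivariate comparions are made, comparing differences between FMT and placebo"; for the questionnaires it is "Bivariate comparisons baseline vs week 4, baseline vs week 8, baseline vs week 26". The blood-sample comparison concerns HbA1c. Nothing elsewhere in the protocol corrects the sentence in section 4.2.

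**The concern.** A random effect suits a factor whose levels are a sample from a larger population and whose spread is of interest, such as patients or centres. Treatment here has two levels, both chosen by design, and the quantity wanted is the difference between them. If treatment is entered as random, the main output is an estimate of how variable treatments are, based on two of them. The difference can be recovered only as a prediction pulled towards zero.

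The protocol justifies the pilot by its use in designing an adequately powered trial (Summary; section 2.6.4). An effect size that is shrunk by construction, and often set to exactly zero, is a poor input for that purpose. The usual form is the reverse of the one written: treatment fixed, patient random. Swapped wording is a likely explanation, but the sentence as it stands prescribes the wrong model.

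**Working it through.** The protocol gives no power, alpha, SD or effect size for this analysis (section 4.1 says there is no basis for a formal calculation), so there is no planned figure to reproduce. The check asks what the stated model returns.

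**Inputs.** 20 patients (section 3.6). 10 per arm, read from the damaged text of Figure 1; section 3.5 states no allocation ratio, so this is an assumption. Further assumptions: normal data, SD = 1, two-sided 5%, and one week-4 change score per patient.

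**Step 1: one simulated data set, both models.** 20 patients, 2 time points, true treatment difference 1.0. Both fits include a patient random effect, so only the role of treatment differs.

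| Role of treatment | What the model reports on treatment |
|---|---|
| Random | Variance 0.417 (SE 0.939); coefficients for intercept and time only |
| Fixed | Contrast 1.01, SE 0.44, 95% CI 0.15 to 1.87, p = 0.021 |

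The variance in the first row rests on 2 − 1 = 1 degree of freedom. Chi-square limits on 1 df run from about 0.2 to 1,018 times the estimate, so it carries almost no information.

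**Step 2: how often the treatment variance is exactly zero.** With n = 10 per arm, the REML estimate is max[0, (MSB − MSW)/n], where MSB and MSW are the between-arm and within-arm mean squares. It is zero whenever F = MSB/MSW < 1. F has 1 and 18 df and non-centrality n·d²/2 = 5d², with d the true effect in SD.
- d = 0: non-centrality 0, P(F < 1) = 0.669
- d = 0.5: non-centrality 1.25, P(F < 1) = 0.429
- d = 0.8: non-centrality 3.2, P(F < 1) = 0.211

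In those trials the predicted FMT-minus-placebo difference is exactly zero.

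**Step 3: shrinkage in the remaining trials.** The observed difference is multiplied by (MSB − MSW)/MSB = 1 − 1/F. At F = 4.41, where the ordinary test just reaches p = 0.05, 1/4.41 = 0.227, so the difference is cut by about 23%.

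**Step 4: average behaviour (20,000 simulated trials per row).** The variance test is the likelihood-ratio test that allows for the zero boundary.

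| True effect (SD) | Mean fixed-effect estimate | Mean random-effect prediction | Rejection, fixed-effect t-test | Rejection, variance test |
|---|---|---|---|---|
| 0 | 0.00 | 0.00 | 4.7% | 2.1% |
| 0.5 | 0.50 | 0.30 | 18.8% | 11.4% |
| 1.0 | 1.00 | 0.79 | 55.9% | 42.4% |
| 1.5 | 1.51 | 1.36 | 88.9% | 80.7% |

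The fixed-effect estimate is unbiased; the prediction is not. The variance test is conservative and says nothing about which arm is better.

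**Step 5: what the corrected model offers at this size.** For a change score the 95% CI half-width is t(0.975, 18) × √(2/10) = 2.101 × 0.447 = 0.94 SD. That is wide, but it is an honest interval on the right quantity.

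**The case against.** The best defence has three parts. The sentence covers 6 of 22 secondary endpoints in a pilot without a power basis. The primary endpoint, grade 2 or higher adverse events in the first week, is not analysed this way. A statistical analysis plan is still to come. All of this stands and limits the severity. It does not remove the point: the protocol has already assigned treatment its role, so a later plan must either inherit the error or depart from the protocol.

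A reader might infer more than the document supports in three places.

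- *That the model yields nothing on treatment.* Shrunken predictions and a non-directional variance test can be extracted, as the table above shows. What is missing is an unbiased FMT-minus-placebo contrast with a confidence interval.
- *That visits are treated as independent patients, inflating false positives.* Repeated measures regression ordinarily means that within-patient dependence is handled, and the exact covariance structure can be left to the analysis plan. Inflation of that kind would need both post-dose visits to be pooled as FMT versus placebo. The protocol does not propose this, and CT and breath test have only one post-dose visit. In a baseline-to-week-4 contrast, ignoring positive within-patient correlation would make intervals too wide, not too narrow.
- *That the bivariate comparisons of diary and questionnaire endpoints are wrong.* Comparing change from baseline between randomised arms is valid. Baseline adjustment may add precision for continuous scores, but several diary endpoints are counts or weekly medians, for which a linear-model gain cannot be assumed.

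It is also fair that the zero-variance percentages come from a single change score with an assumed 10 per arm, and not from the full repeated-measures model. They illustrate the size of the problem; the conclusion does not depend on them.

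**Conclusion.** The point holds, confined to the WMC, CT and breath-test endpoints (14 to 19). Section 4.2 puts treatment in the wrong part of the model, and no other section corrects it. Under the assumptions listed, the stated approach would set the treatment effect to exactly zero in about two thirds of trials with no effect, 43% at 0.5 SD and 21% at 0.8 SD, and would shrink it in the rest. That a two-level treatment entered as random does not give the contrast wanted in section 3.1 follows from the model and needs none of those assumptions.

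This is a should-fix. The error is one of stated method, not of omitted detail, but it affects secondary endpoints of a pilot and leaves the primary safety endpoint untouched.

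**What to change.** Replace the sentence in section 4.2 with wording such as: WMC, low-dose CT and breath-test data will be analysed with a linear mixed model with fixed effects for randomised arm, visit and arm-by-visit, adjusted for the baseline value, and with patient as the random (repeated-measures) effect; the FMT-versus-placebo estimate is the arm difference at week 4 with its 95% CI.

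Two clarifications belong with it.
- CT and breath test have a single post-baseline visit, so for them the model reduces to ANCOVA on the baseline value.
- For WMC after the second intervention both arms have received FMT. Report that contrast as two doses versus one (hypothesis 4 in section 2.3.2), not as FMT versus placebo.

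Baseline adjustment of continuous questionnaire and diary scores is optional.

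The cost is one sentence in the protocol, carried into the analysis plan before unblinding, and one degree of freedom for the baseline covariate. No new data, visits or patients are needed.

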# 5.0 Participants

The Danish organisation "Diabetesforeningen" has estimated that there are 28.000 people in Denmark with type DM1. Several studies provide evidence that DM1 is associated with an increased prevalence of lower and upper gastrointestinal symptoms. However, the prevalence of patients with DM1 and severe gastrointestinal neuropathy is unknown. Judged from clinical experience in the tertiary centers at AUH And AAUH we believe it possible to find 20 patients who are willing to participate in the study.

# 5.1 Inclusion criteria

- Adult ( $\geq$  18 years old), male or female patients with DM1 for at least 5 years and
- Average of or above 40 points in the questionnaire: Gastrointestinal syndrome rating scale irritable bowel syndrome version (GSRS-IBS).

# 5.2 Exclusion criteria

- Inability to understand Danish or the trial procedures
- Known or anticipated pregnancy (excluded by male sex, postmenopausal women and otherwise negative U-HCG)
- Known severe renal insufficiency (eGFR < 20 mL/min)
- Antibiotic use in the prior 4 weeks
- Patients with recent changes in morphine treatment (within the last 4 weeks)
- Ongoing infection with *Clostridioides difficile* or pathogenic intestinal bacteria or parasites (negative PCR test)
- Known gastrointestinal disease or GI infection (diagnosed with celiac disease, inflammatory bowel disease, infection and gastrointestinal cancer)
- Patients with dysregulated thyroid disease (abnormal TSH)
- Patients diagnosed with intestinal stricture
- Patients with other known disorder that can cause gastroparesis (ex. Parkinson's and scleroderma)
- Patients with planned MR scan within 4 weeks
- Patients with pacemaker/ICD
- Previous abdominal surgery (minor surgical procedures ex. appendectomy allowed)
- Changes in medicine that affects the GI tract in the prior 4 weeks

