#### **3.6.1** Information and inclusion (visit 1)

Potentially eligible patients are informed about the project and offered  $\geq$ 24h to consider participation. If the patients are willing to participate in the study, and they meet the in- and exclusion criteria, they will sign the ICF. If eligible, they will be assigned a unique study number and randomised to either active FMT or placebo. The patients will receive a bowel habit diary, a collection kit for faecal samples and a schedule for the study period.

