#### 6.1.1.3 Wireless Motility Capsule

The WMC is an orally ingested data recording device that enables simultaneous assessment of regional and whole gut transit. The WMC is CE marked and approved by the US Food and Drug Administration for evaluation of patients with suspected delayed gastric emptying and evaluation of colonic transit time in patients with chronic constipation. The WMC is contraindicated to patients with a history of gastric bezoar, swallowing disorders, dysphagia to food or pills, suspected

stricture or fistulae along the GI tract, physiological GI obstruction, GI surgery within the previous 3 months, Crohn's disease, diverticulitis or an implanted or portal electromechanical medical device(31).

The most serious AEs associated with the WMC are the inability to confirm passage of the capsule outside the body, capsule retention and obstruction. In a previous trial with nearly 6000 patients receiving WMC there were 20 reports of prolonged capsule retention (5 in the stomach, 2 in the small intestine and 13 in the colon) which yield a retention rate of 0,33%(30). An upper endoscopy was required for extraction of the 5 capsules that were retained in the stomach. Of the remaining 15 cases, only 1 capsule required drug intervention. The other 14 capsules passed spontaneously. None of the patients required surgical intervention. If it cannot be confirmed that the capsule has passed five days after ingestion the manufacturer's follow-up recommendations should be followed. This is based on the location of the capsule which is determined by the pH profile obtained during the study. If the pH profile suggests that the capsule is retained in the stomach or bowel. Due to the low risk of obstruction once the capsule is in the colon, no specific follow-up is necessary if the capsule is retained in this area.

Other side effects associated with WMC include abdominal pain, dysphagia, nausea and diarrhea. However, as many of the patients had these symptoms at baseline, these side effects have been difficult to determine if they were caused by the WMC. Patients are provided information about the risks in the participants information sheet, which they are urged to read comprehensively prior to consenting to participate.

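### The exclusion criteria in 5.2 are narrower than the protocol's own wireless motility capsule contraindications in 6.1.1.3, so an eligible patient can be randomised and then be barred from a scheduled procedure

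*Protocol*

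**What the plan says.** Section 6.1.1.3 of the protocol states the contraindications in one sentence. It begins "The WMC is contraindicated to patients with a history of gastric bezoar, swallowing disorders, dysphagia to food or pills", goes on to suspected "stricture or fistulae along the GI tract, physiological GI obstruction, GI surgery within the previous 3 months", and ends with Crohn's disease, "diverticulitis or an implanted or portal electromechanical medical device".

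Section 5.2 has four exclusion criteria that touch this list:

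- "Patients with pacemaker/ICD"
- "Patients diagnosed with intestinal stricture"
- "Previous abdominal surgery (minor surgical procedures ex. appendectomy allowed"
- "Known gastrointestinal disease or GI infection (diagnosed with celiac disease, inflammatory bowel disease, infection and gastrointestinal cancer"

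Section 3.6.1 sets the order of events at visit 1: "If eligible, they will be assigned a unique study number and randomised to either active FMT or placebo". Table 1 puts the criteria check, the medical history and randomisation all at that visit. The first WMC follows at visit 2, and Table 1 repeats it at visits 5 and 8. The text for those visits describes no contraindication check and no provision for a patient to skip the capsule.

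**The concern.** The capsule is part of the schedule for everyone. A patient who may not swallow it should therefore be identified by the list that decides entry. Section 5.2 already does part of this job, since it excludes stricture and pacemaker or ICD, but it stops short of the list in 6.1.1.3.

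If such a patient passes 5.2 and is not noticed, the capsule may be given against 6.1.1.3. If the patient is noticed after randomisation, the capsule is withheld. Section 5.4 does not make a missing WMC a reason for discontinuation, so that patient stays in and counts toward the 20. The patient then has no transit times and no pH drop (endpoints 14 to 16 in 2.4.2). Nor can the patient be classed as having normal or prolonged gastric emptying and small intestinal transit, which 3.3.2 gives as a purpose of the baseline recording.

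**Working it through.** No sample-size or error-rate formula applies. The check sets the two lists side by side.

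| Contraindication in 6.1.1.3 | Nearest item in 5.2 | Match |
|---|---|---|
| Crohn's disease | inflammatory bowel disease | covered |
| Stricture, suspected, anywhere in the GI tract | diagnosed, intestinal only | narrower |
| Implanted or portal electromechanical device | pacemaker or ICD | narrower |
| GI surgery in the last 3 months | abdominal surgery at any time, minor procedures allowed | stricter in general, open for recent minor procedures |
| Fistula | known gastrointestinal disease | depends on reading |
| Physiological obstruction | known gastrointestinal disease | depends on reading |
| Diverticulitis | known gastrointestinal disease | depends on reading |
| Gastric bezoar | none named | not named |
| Swallowing disorder; dysphagia | none named | not named |

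**Count.** With swallowing disorder and dysphagia taken together, since they overlap, there are 1 + 3 + 3 + 2 = 9 rows: one covered, three narrower, three depending on the reading and two not named. Listing the two separately gives 10.

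**Sensitivity to the reading.**

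- If known gastrointestinal disease takes in fistula, obstruction and diverticulitis, 4 rows are covered and 3 + 2 = 5 still show a gap.
- If the bracketed list is exhaustive, 1 row is covered, 3 are narrower and 5 are not named.

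The broad reading cannot be unlimited, because the trial enrols patients for severe gastrointestinal neuropathy. Something has to limit that item, and the brackets are the only limit written.

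**What one admitted patient would mean.**

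- Scheduled ingestions: visits 2, 5 and 8 = 3.
- WMC endpoint values lost if the capsule is withheld throughout: 3 endpoints × 3 time points = 9.
- Share of the planned WMC sample: 1/20 = 5%. Share of one arm of 10 (Figure 1): 1/10 = 10%.

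**Retention rate.** The protocol's own figure reproduces: 20 reports in nearly 6000 patients is 20/6000 = 0.33%. This is a background rate among WMC users in general. It says nothing about contraindicated patients and so does not measure the gap.

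**The case against.** The strongest reply is that the protocol already forbids the unsafe act. Section 6.1.1.3 is protocol text, and giving the capsule to a listed patient would go against it whatever 5.2 says. A reader might infer from the mismatch that the trial permits the capsule in contraindicated patients. It does not, and that reading should be dropped.

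The chance of late discovery is also lower than the two lists alone suggest. Patients are worked up and seen by a gastroenterologist (5.3), a medical history is taken at visit 1 (Table 1), and only trained personnel handle the equipment (6.1). Many such patients would probably be recognised before randomisation. This stands as mitigation. However, the work-up in 5.3 is aimed at competing gastrointestinal disease, and nothing in 5.2 tells staff to exclude a patient because of a swallowing disorder or a past bezoar.

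It is also fair to say that a bare count of unmatched items overstates the problem. Some items overlap, the surgery criterion is mostly stricter than 6.1.1.3, and an ordinary reading of known gastrointestinal disease reaches some of the rest. A generous reader might stretch it to a bezoar, or to dysphagia with a diagnosed cause. Even then, suspected stricture, other devices, recent minor surgery and dysphagia without a diagnosed gastrointestinal disease remain open.

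Finally, one might extend the point to the FMT capsules, of which a single treatment contains about 22 (3.2.1). That is a separate matter. The list in 6.1.1.3 concerns the WMC, and the protocol nowhere makes dysphagia a contraindication to FMT capsules.

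**Conclusion.** The two sections conflict, and the conflict is worth fixing. Section 5.2 as written can randomise a patient whom 6.1.1.3 bars from a procedure scheduled three times. On the reading most favourable to 5.2 in the working, gaps remain for bezoar, swallowing disorder or dysphagia, suspected or non-intestinal stricture, devices other than pacemaker or ICD, and recent minor surgery. This part rests on the text alone.

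The consequence is modest and cannot be put as a rate. The protocol gives neither the number of such patients nor their retention risk, so the 5% and 10% above describe one hypothetical patient and are not a forecast. The endpoints at stake are secondary, in a pilot without a formal power calculation. A reader might infer that the safety conclusion is compromised. The documents do not support that, because the primary endpoint counts adverse events of grade 2 or more in the first week after the first intervention and needs no WMC recording.

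**What to change.** Add one exclusion criterion to 5.2, checked at visit 1 before randomisation: any WMC contraindication in 6.1.1.3. Spell it out as:

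- past gastric bezoar;
- swallowing disorder, or dysphagia for food or pills;
- stricture or fistula, suspected or diagnosed, at any level of the GI tract;
- physiological GI obstruction;
- GI surgery of any size, minor included, in the preceding 3 months;
- Crohn's disease;
- diverticulitis;
- an implanted electromechanical device.

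Worn devices need an explicit decision. The protocol does not mention insulin pumps or glucose sensors. That patients in this population may wear them, and that the word portal in 6.1.1.3 may be meant to include them, are assumptions. The criterion should say, in line with the manufacturer's labelling, whether they count, and should not exclude their users by default.

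State also that if a contraindication arises after randomisation, the capsule is omitted and the patient stays in the trial. This fits 5.4, which does not list a missing capsule as a reason for discontinuation.

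The cost is a short amendment and the exclusion of a few otherwise eligible patients. The number would be larger if worn devices were counted.
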